## 8. SELECTION OF PATIENTS

### 8.1. Number of Patients

Approximately 210 patients will be enrolled overall, including ~160 patients with penta-refractory MM (Part 1 [~30] and Part 2 [~130]) and ~50 patients with quad-refractory MM (Part 1 only). See Section 7.1.

### 8.2. Recruitment

This study will be conducted at multiple sites in the United States and Europe.

### 8.3. Documentation Requirements

For enrollment consideration, patients may be eligible if they have *documented evidence* of previous treatment for MM that substantiates disease status as follows:

- Refractory to a glucocorticoid
- Refractory to lenalidomide and/or pomalidomide (only 1 required) *and* evidence of prior treatment\* with *both* lenalidomide and pomalidomide
- Refractory to bortezomib and/or carfilzomib (only 1 required) *and* evidence of prior treatment\* with *both* bortezomib and carfilzomib
- Refractory to daratumumab

\* Prior treatment is defined as either refractory, treatment with  $\geq 2$  cycles, or documented severe intolerance.

Documented evidence will include at least one of the following:

1. Medical records that support start and stop dates (month/year) of prior treatment (both dose and schedule), best response on prior treatment and, if applicable, date of progression (including both dose and schedule at the time of progression).
2. Myeloma marker values (SPEP, UPEP, Immunoglobulin, FLC) at the time of prior treatment start, stop and time of progression (accompanied by #1).
3. Formal, signed physician letter by Investigator (on hospital/clinic letterhead), to be included in the patient's medical and research record, indicating start/stop dates of prior treatment (both dose and schedule), best response on treatment and, if applicable, date of progression (including both dose and schedule at the time of progression).
4. Formal, signed physician letter from referring physician (on hospital/clinic letterhead), to be included in the patient's medical and research record, that includes prior treatment history indicating start/stop dates of prior treatment (both dose and schedule), best response on prior treatment and, if applicable, date of progression (including both dose and schedule at the time of progression).

## 8.4. Inclusion Criteria

Patients must meet all of the following inclusion criteria to be eligible to enroll in this study:

1. Written informed consent in accordance with federal, local, and institutional guidelines.
2. Age  $\geq$  18 years at the time of signing informed consent.
3. Measurable MM based on IMWG guidelines as defined by at least one of the following:
  - a. Serum M-protein  $\geq$  0.5 g/dL by serum electrophoresis (SPEP) or, for IgA myeloma, by quantitative IgA
  - b. Urinary M-protein excretion  $\geq$  200 mg/24 hours
  - c. FLC  $\geq$  100 mg/L, provided that the FLC ratio is abnormal.
  - d. If serum protein electrophoresis is felt to be unreliable for routine M-protein measurement, then quantitative Ig levels by nephelometry is acceptable.
4. Patients must have previously received  $\geq$  3 anti-MM regimens including: an alkylating agent, lenalidomide, pomalidomide, bortezomib, carfilzomib, daratumumab, and a glucocorticoid. There is no upper limit on the number of prior therapies provided that all other inclusion/exclusion criteria are met.
5. MM refractory to previous treatment with one or more glucocorticoids, parenteral PI (i.e., bortezomib and/or carfilzomib), IMiD (i.e., lenalidomide and/or pomalidomide), and daratumumab. Refractory is defined as  $\leq$  25% response to therapy, or progression during therapy or progression within 60 days after completion of therapy.
6. Multiple myeloma that is refractory to the patient's most recent anti-MM regimen. (Documented severe intolerance to the patient's last therapy is allowed upon approval by the Medical Monitor.)
7. Any clinically significant non-hematological toxicities (except for peripheral neuropathy as described in exclusion criterion #17) that patients experienced from treatments in previous clinical studies must have resolved to Grade  $\leq$  2 by Cycle 1 Day 1.
8. Adequate hepatic function within 21 days prior to Cycle 1 Day 1: total bilirubin  $<$  2x upper limit of normal (ULN) (except patients with Gilbert's syndrome who must have a total bilirubin of  $<$  3x ULN), AST  $<$  2.5x ULN and ALT  $<$  2.5x ULN.
9. Adequate renal function within 21 days prior to Cycle 1 Day 1: estimated creatinine clearance of  $\geq$  20 mL/min, calculated using the formula of Cockcroft and Gault.
10. Female patients of childbearing potential must agree to use 2 methods of contraception (including 1 highly effective and 1 effective method of contraception) and have a negative serum pregnancy test at Screening. Male patients must use an effective barrier method of contraception if sexually active with a female of child-bearing potential. For both male and female patients, effective methods of contraception must be used throughout the study and for three months following the last dose of study treatment.

11. Eastern Cooperative Oncology Group (ECOG) Performance Status of  $\leq 2$ .
12. Adequate hematopoietic function within 21 days prior to Cycle 1 Day 1 (See Exclusion Criterion #20 for transfusion washout periods for RBCs and platelets):
  - a. Total WBC count  $> 1,000/\text{mm}^3$
  - b. ANC  $\geq 1000/\text{mm}^3$
  - c. Platelet count  $\geq 75,000/\text{mm}^3$  (patients in whom  $<50\%$  of bone marrow nucleated cells are plasma cells) or  $\geq 50,000/\text{mm}^3$  (patients in whom  $\geq 50\%$  of bone marrow nucleated cells are plasma cells. (Platelet transfusions  $< 1$  week prior to Cycle 1 Day 1 are prohibited [see below].)
13. Hemoglobin level  $\geq 8.5$  g/dL. In certain cases, patients with stable baseline hemoglobin level  $> 8.0$  may be included following approval by the Medical Monitor. (Red blood cell transfusions  $< 2$  weeks prior to Cycle 1 Day 1 are prohibited [see below].)
14. Confirmation of patient eligibility for specific key criteria for study participation with the Medical Monitor.

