## 5. RATIONALE FOR THE STUDY

Multiple myeloma is the second most common hematological malignancy. With conventional treatment methods, median survival is 5.2 years after diagnosis (*Kumar 2014*). Multiple myeloma is highly treatable but is not considered to be curable with currently available therapies. Common treatments include glucocorticoids, chemotherapy, proteasome inhibitors, immunomodulatory drugs, stem cell transplants, and radiation therapy.

Selinexor has demonstrated anti-MM activity in pre-clinical studies *in vitro* and *in vivo*. A summary of clinical results for 81 patients with MM seen in Study KCP-330-001, as of 01 August 2016, is provided in Section 4.3.

The original design of this protocol (KCP-330-012) was based on the primary treatment options for RR MM (i.e., IMiDs and PIs) that were in common use at the time that the protocol was developed, in order to evaluate whether selinexor would provide a useful, new therapeutic option to patients whose disease was RR to these treatments (i.e., patients with quad-refractory MM). In that design, a subset of patients with penta-refractory MM was also included as an **CCI**, as treatment with anti-CD38 mAbs was not yet common. With the recent approval of daratumumab and ongoing development of isatuximab, the clinical use of anti-CD38 mAbs to treat RR MM has become more common, suggesting that selinexor would be best considered as a therapeutic option in patients with penta-refractory MM.

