## 8.5. Exclusion Criteria

1. Active smoldering MM.
2. Active plasma cell leukemia.
3. Documented systemic amyloid light chain amyloidosis.
4. Active central nervous system (CNS) MM.
5. Pregnancy or breastfeeding.
6. Radiation, chemotherapy, or immunotherapy or any other anticancer therapy  $\leq 2$  weeks prior to Cycle 1 Day 1, and radio-immunotherapy 6 weeks prior to Cycle 1 Day 1.
7. Active graft vs. host disease (after allogeneic stem cell transplantation) at Cycle 1 Day 1
8. Life expectancy of  $< 4$  months.
9. Major surgery within four weeks prior to Cycle 1 Day 1.
10. Active, unstable cardiovascular function:
  - a. Symptomatic ischemia, or
  - b. Uncontrolled clinically-significant conduction abnormalities (e.g., patients with ventricular tachycardia on antiarrhythmics are excluded; patients with 1st degree atrioventricular (AV) block or asymptomatic left anterior fascicular block/right bundle branch block (LAFB/RBBB) will not be excluded), or
  - c. Congestive heart failure (CHF) of New York Heart Association (NYHA) Class  $\geq 3$ , or
  - d. Myocardial infarction (MI) within 3 months prior to Cycle 1 Day 1.
11. Active, uncontrolled hypertension.

12. Uncontrolled active infection requiring parenteral antibiotics, antivirals, or antifungals within one week prior to first dose.
13. Known HIV seropositive.
14. Known active hepatitis A, B, or C infection; or known to be positive for HCV RNA or HBsAg (HBV surface antigen).
15. Prior malignancy that required treatment, or has shown evidence of recurrence (except for non-melanoma skin cancer or adequately treated cervical carcinoma in situ) during the 5 years prior to enrollment. Cancer treated with curative intent > 5 years previously and without evidence of recurrence will be allowed.
16. Active GI dysfunction interfering with the ability to swallow tablets, or any GI dysfunction that could interfere with absorption of study treatment.
17. Grade  $\geq 3$  peripheral neuropathy, and Grade  $\geq 2$  painful neuropathy, within 21 days prior to Cycle 1 Day 1.
18. Serious, active psychiatric or medical conditions which, in the opinion of the Investigator, could interfere with treatment.
19. Participation in an investigational anti-cancer study within 21 days prior to Cycle 1 Day 1.
20. Receipt of transfusions as follows:
  - a. Platelet infusion within 1 week prior to Cycle 1 Day 1.
  - b. RBC transfusion within 2 weeks prior to Cycle 1 Day 1.

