#### Amendment Rationale

The primary purpose for this amendment is to:

- Address the following FDA deficiency and comments provided in an e-mail message with the subject: “IND-114042 KPT-330-Deficiency and Comments”, dated: 21Jan2014:
  - Deficiency:
    - To be eligible for the trial, patients should have returned to  $\leq$  Grade 2 non hematological toxicities from previous treatment.
  - Comments:
    - The primary endpoint should be per central independent review committee including radiology review.
    - Time-to-event endpoints such as PFS/OS and Patient Reported Outcomes are not evaluable in non-controlled trials.

The revised protocol Version 2.0, dated 05Feb2015 will be submitted by the Principal Investigator(s) to all applicable Institutional Review Boards (IRBs), Independent Ethics Committees (IECs), or Research Ethics Boards (REBs), and by Karyopharm Therapeutics Inc. to all applicable Regulatory Authorities.

A summary of key changes that were made to protocol Version 1.0, including rationales for these changes, is provided below.

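### Inclusion 7 requires recovery only from toxicity of therapy given in earlier clinical studies, which leaves a partial gap for toxicity from non-trial therapy

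*Protocol*

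**What the plan says.** Inclusion 7 appears in the same words in the synopsis and in Protocol Section 8.4. Its subject is "Any clinically significant non-hematological toxicities (except for peripheral neuropathy as described in exclusion criterion #17"), limited to those "that patients experienced from treatments in previous clinical studies must have resolved to Grade" 2 or lower by Cycle 1 Day 1.

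The surrounding text bears on that limit as follows.

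- **Inclusion 4** asks for at least three "anti-MM regimens including: an alkylating agent, lenalidomide, pomalidomide, bortezomib, carfilzomib, daratumumab, and a glucocorticoid". It does not say that any of these was given in a study.
- **Section 5** expects use outside trials: "With the recent approval of daratumumab and ongoing development of isatuximab, the clinical use of anti-CD38 mAbs to treat RR MM has become more common".
- **Inclusion 6** requires disease refractory to the latest regimen, with one exception: "Documented severe intolerance to the patient's last therapy is allowed upon approval by the Medical Monitor".
- **Exclusion 16** bars "Active GI dysfunction interfering with the ability to swallow tablets, or any GI dysfunction that could interfere with absorption of study treatment".
- **Exclusion 18** bars "Serious, active psychiatric or medical conditions which, in the opinion of the Investigator, could interfere with treatment".
- **Appendix 7, Amendment 1 rationale**, records the regulator's deficiency as a return to at most "Grade 2 non hematological toxicities from previous treatment". This is a log entry about superseded text. It shows what the criterion was written for and nothing more.

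**The concern.** Take two patients with the same unresolved Grade 3 non-hematological toxicity from the same drug. One received it in a trial and fails inclusion 7. The other received it in routine care and passes. The setting in which a drug was given does not change the risk of starting a new regimen on top of its toxicity, and the documents give no reason for the distinction.

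Three things are at stake.

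- **Patient safety at entry.** Protocol Section 4.3.1.4 reports treatment-related fatigue in 64% of patients (Grade 3 in 14%) and nausea in 68% (Grade 3 in 8%). A patient may start this regimen with severe toxicity that the sponsor's own recovery requirement would have held back had it arisen in a trial.
- **Consistency of eligibility.** A site that follows the wording and a site that follows the evident purpose will decide differently about the same patient.
- **Reading of adverse events.** Protocol Section 13.3.7.1 and SAP Section 5.1.1 count worsening of a pre-existing condition as treatment-emergent. With a single arm, there is no control group to show how much of that is carried over.

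**Working it through.** This is a question of scope, so there is no figure to reproduce and no arithmetic to run. The check compares the texts.

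**1. What does inclusion 7 reach?** Three conditions must all hold: the toxicity is clinically significant and non-hematological, it is not peripheral neuropathy, and it came from treatment in a previous clinical study. The third condition makes it source-dependent.

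**2. Can the required prior therapy fall outside it?** Yes. Inclusion 4 names agents and a minimum number of regimens, not a setting. Section 5 describes growing clinical use of anti-CD38 antibodies.

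**3. Does another criterion restore the requirement for non-trial therapy?** No criterion sets a general graded limit. The following apply whatever the source of the toxicity.

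| Criterion (Protocol 8.4, 8.5) | What it catches | What it leaves |
|---|---|---|
| Inclusion 8, 9 | Hepatic and renal toxicity beyond stated laboratory limits | Other organs |
| Inclusion 11 | Toxicity that pushes ECOG status above 2 | Severe toxicity compatible with ECOG 2 or better |
| Exclusion 10, 11, 12 | Unstable cardiovascular function, uncontrolled hypertension, uncontrolled infection | Other organs |
| Exclusion 16 | GI dysfunction affecting swallowing or absorption | Other GI toxicity |
| Exclusion 17 | Neuropathy, by grade, from any source | Nothing within its own subject |
| Exclusion 18 | Serious active conditions the Investigator thinks could interfere | Has no grade, so depends on judgement |

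Inclusions 12 and 13 concern blood counts and hemoglobin, which inclusion 7 does not cover.

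**4. What is left?** Grade 3 or higher non-hematological toxicity from non-trial therapy, in an organ with no criterion of its own, compatible with ECOG 2 or better, and not judged disqualifying under exclusion 18. Grade 3 skin toxicity and GI toxicity that spares swallowing and absorption are examples that may not be caught.

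**5. Does the washout fill the gap?** No. Exclusion 6 asks for more than 2 weeks since any anticancer therapy. Exclusion 19 asks for 21 days since participation in an investigational anti-cancer study. Both set time elapsed, not recovery. The patient coming from a trial has the longer wait and the recovery requirement. The patient coming from routine care has the shorter wait and, under inclusion 7, no recovery requirement.

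**6. Is the narrow scope the recorded purpose?** The Amendment 1 rationale speaks of previous treatment without limiting it to studies. The log line on the resulting change to the inclusion criteria also refers to previous treatments, although it names hematologic rather than non-hematological toxicity. The log is thus unclear about the type of toxicity, but neither entry limits the source.

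**The case against.** The strongest reply is that the rest of the eligibility section does most of the work. The criteria in the table apply regardless of source. A carfilzomib toxicity that is cardiac, renal, hepatic or hypertensive would meet one of them. ECOG limits entry with severe functional toxicity such as fatigue. Inclusion 14 adds Medical Monitor confirmation of key criteria. This stands, and it is why the gap is described as partial. It does not close the gap: exclusion 18 has no grade, inclusion 14 does not say which criteria are key, and confirming a patient against inclusion 7 as worded would pass the cases in question.

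A second reply is that an amendment log cannot convict current text, particularly as several protocol versions followed and the documents do not show why the present wording was chosen. That is also right. The log is evidence of purpose only, and its difference from inclusion 7 is not itself an error.

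A reader might be tempted by three stronger readings that the documents do not support.

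- **That many patients are affected.** The documents give neither the share of prior regimens received in trials nor the frequency of unresolved Grade 3 or higher toxicity at entry. An assumed trial share would measure only how often inclusion 7 is silent, not how many patients carry toxicity that nothing else catches.
- **That inclusion 6 makes recent severe toxicity likely.** Its exception needs Medical Monitor approval, and past intolerance is not the same as toxicity still present on Cycle 1 Day 1.
- **That ORR is distorted.** The mITT population keeps patients who stop for toxicity, so any effect of early stopping would run against the drug. Its size is speculative.

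Finally, worsening of Grade 1 or 2 toxicity already present at entry would still count as treatment-emergent after the change. The fix limits carried-over toxicity but does not remove it.

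**Conclusion.** The point holds as one of scope. Inclusion 7 makes an existing safety requirement depend on whether earlier therapy was given in a clinical study, no reason is stated, and no other criterion supplies a general graded limit for therapy given elsewhere. The exposure is confined to clinically significant non-hematological toxicity of Grade 3 or higher that the source-neutral criteria miss. How many patients that is cannot be derived from the documents, and it may be small. No effect on the primary test against the 10% threshold is shown.

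The conclusion rests on reading inclusion 7 literally. If sites have in practice applied it to all previous therapy, the harm is limited to the wording and to possible inconsistency between sites. It is a worthwhile, inexpensive correction and not a threat to the trial's main conclusion.

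**What to change.** Reconcile the scope of inclusion 7 with its recorded purpose, in Section 8.4 and in the synopsis together, so that the sponsor's existing requirement no longer depends on the setting of the earlier therapy. One way is to refer to previous treatment in general in place of treatment in previous clinical studies. The sponsor's own grade limit, the Cycle 1 Day 1 time point and the neuropathy exception stay as they are. If the limit to studies was intended, the protocol should say why.

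The text change is a few words. Protocol Section 9.1.2 already collects baseline symptoms and earlier discontinuations for intolerability or toxicity, so little extra data collection should be needed. A few patients would wait longer or fail screening.

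The less obvious cost is timing. Part 2 enrolls under Version 4.0 (11 August 2016) and later, and Version 6.0 is dated 13 December 2017, 16 months afterwards. A change made during Part 2 means that mITT patients enrolled before and after it enter under different wording. The amendment date should be recorded so that the two groups can be told apart in the report.

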Adverse events 	X	X	X	X	X	X	X	X	X	X	
Concomitant medications	X	X	X	X	X	X	X	X	X		
Nutritional consultation	X										
Telephone contact 			X							X	X
Antineoplastic therapy after EoT									X	X	X

(X) indicates that additional information is provided in the footnotes. Merged cells indicate that the procedure may be performed during either Screening or the C1D1 visit.

Abbreviations: BSA = body surface area; ECG = electrocardiogram; ECOG = Eastern Cooperative Oncology Group; EoT = End of Treatment; Ig = immunoglobulin; MM = multiple myeloma; SPEP = serum protein electrophoresis; UPEP = urine protein electrophoresis; CBC = complete blood count; FLC = free light chain.

 Prior to the first study-specific measure.

 Including details of all prior anti-myeloma therapies. Includes baseline symptoms as well as a detailed history of prior cancer therapies, especially MM therapies, including start and stop dates, disease progression during or after therapy, as well as discontinuations due to intolerability or any other serious illness. Results of pre-screening MM assessments at Day -30 (window: Screening – 2 weeks) and Day -60 ( $\pm 15$  days) will be provided.

 Body Surface Area (BSA) will be calculated by *Dubois 1916* or *Mosteller 1987* method during Screening and prior to any dose escalation. No patient may receive a dose of selinexor  $> 70$  mg/m^2.

 Complete physical examination (PE) during Screening and EoT visit. Limited PEs during the study should be symptom directed. All PEs to include vital signs (blood pressure, pulse and body temperature).

 The following procedures may be performed at Screening or pre-dose on C1D1 and as shown in the Schedule during the study: ECOG performance assessment, echocardiogram or MUGA scan, 12-lead ECG, ophthalmic exam, urinalysis, CBC with differential, TSH, complete serum chemistry, coagulations tests, and nutritional consultation.

 Echocardiogram or MUGA scan at Screening and as clinically indicated during the study.

 A full ophthalmic examination will include, prior to dilation, best corrected visual acuity, slit lamp examination including tonometry, following dilation; funduscopy and slit lamp to document lens clarity.

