21. Receipt of the following blood growth factors within 2 weeks prior to Cycle 1 Day 1: Granulocyte colony stimulating factor (G-CSF), granulocyte-macrophage colony stimulating factor (GM-CSF), erythropoietin (EPO), or megakaryocyte growth factor.
22. Known intolerance to or contraindications for glucocorticoid therapy at Cycle 1 Day 1.
23. Prior exposure to a SINE compound, including selinexor.
24. Unable or unwilling to comply with protocol requirements, including providing a 24-hour urine samples at the required study time points.

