#### Inclusion/Exclusion Criteria (also in Synopsis and Sections 8.4 and 8.5)

- Modified inclusion criteria #10 to clarify that female patients of childbearing potential must agree to use 2 methods of contraception (including 1 highly effective and 1 effective method of contraception).
- Modified inclusion criteria #13 to remove “on Cycle 1 Day 1” for hemoglobin level  $\geq$  8.5 g/dL.

- Modified inclusion criteria #14 to add “key” to specific criteria.
- Corrected exclusion criteria #17 to add  $\geq$  to Grade 2 painful neuropathy

**Table 1 (Schedule of Assessments)** (also in Section 9.7.2.4)

- Modified footnote #8 to, “For females of childbearing potential; negative serum hCG pregnancy test must be obtained within 3 days before the first dose of study treatment. Pregnancy testing (serum hCG or urine) is also required for females of childbearing potential prior to dosing on Day 1 of Cycles  $\geq$  2 and at the EoT Visit (serum hCG). Pregnancy testing may also be performed as clinically indicated during the study,” to required that testing is performed on Day 1 of Cycles  $\geq$  2.

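### Transfusion and growth-factor washouts count back from Cycle 1 Day 1, not from the qualifying blood count, so a patient can meet every criterion on a supported count

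*Protocol*

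**What the plan says.** Four places in the protocol bear on this. The synopsis repeats the criteria.

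- **Inclusion 12 (Section 8.4)** sets floors for white cells, neutrophils and platelets: "Adequate hematopoietic function within 21 days prior to Cycle 1 Day 1 (See Exclusion Criterion #20 for transfusion washout periods for RBCs and platelets". It refers to exclusion 20 but not to exclusion 21. Item 12c repeats the platelet-transfusion ban.
- **Inclusion 13 (Section 8.4)** sets a hemoglobin floor of 8.5 g/dL, with an exception that begins "In certain cases, patients with stable baseline hemoglobin level" (above 8.0, with approval). It repeats the red-cell ban and gives no sampling date. The Version 5.0 entry in Appendix 7 shows that the date was taken out: "Modified inclusion criteria #13 to remove “on Cycle 1 Day 1” for hemoglobin level".
- **Exclusions 20 and 21 (Section 8.5)** bar "Platelet infusion within 1 week prior to Cycle 1 Day 1", "RBC transfusion within 2 weeks prior to Cycle 1 Day 1" and "Receipt of the following blood growth factors within 2 weeks prior to Cycle 1 Day 1".
- **Table 1, footnote 5** covers the CBC among other baseline procedures: "The following procedures may be performed at Screening or pre-dose on C1D1 and as shown in the Schedule during the study".

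Appendix 7, in the entry for protocol Version 4, gives the reason for adding exclusions 20 and 21: to secure adequate blood-cell production at baseline.

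**The concern.** The washouts and the count floors serve one stated aim, which is that the patient's own marrow function is adequate at baseline. They are tied to different dates. The washout is measured to Cycle 1 Day 1 (C1D1), while the count may be up to three weeks older. A count taken soon after a transfusion or a growth-factor dose can satisfy the floor, and the support can still lie outside the barred interval by the time of first dosing. No later pre-dose count is required.

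Two things are at stake. The first is entry screening: protocol Section 4.3.1.4 reports treatment-related Grade 3/4 thrombocytopenia in 51% of 92 patients in this study at the 31 March 2017 cut-off, so the platelet floor matters. The second is the safety baseline. SAP Section 2.5 takes the latest value before first dose, and protocol Section 13.3.7.2 substitutes the Screening value when no Day 1 value exists. A supported Screening count can then become the reference for the CTCAE shift tables (protocol Section 13.3.7.2, SAP Section 5.3.2).

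**Working it through.** The plan states no figure on this point, so the check is a day count.

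**Inputs.** Day -n is n days before C1D1 (there is no Day 0, SAP Section 2.4). The qualifying count may fall on Day -21 to Day -1 or pre-dose on C1D1 (inclusion 12; Table 1 and footnote 5). The washout W is 7 days for platelet transfusion and 14 days for red cells and growth factors (exclusions 20 and 21).

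**Formulas.** Exclusions 20 and 21 bar support within W days, so the last permitted day is Day -(W+1). Criteria 12c and 13 use a less-than sign, which moves it to Day -W. A count directly follows permitted support if it is drawn after that support on the same day. The number of such count days is 21 - W on the first reading and 22 - W on the second. A count day is fully covered if it lies at least W days after the last permitted day.

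| Support and count | W | Reading | Last permitted day | Count days directly after permitted support | Fully covered count days |
|---|---|---|---|---|---|
| Platelet transfusion, platelet count | 7 | within | -8 | -21 to -8: 21 - 7 = 14 | -1 and C1D1 |
| same | 7 | less than | -7 | -21 to -7: 22 - 7 = 15 | C1D1 |
| Red cells, hemoglobin | 14 | within | -15 | -21 to -15: 21 - 14 = 7 | -1 and C1D1 |
| same | 14 | less than | -14 | -21 to -14: 22 - 14 = 8 | C1D1 |
| Growth factor, the count it raises | 14 | within | -15 | -21 to -15: 21 - 14 = 7 | -1 and C1D1 |

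The red-cell rows assume that hemoglobin is drawn in the Table 1 window, because criterion 13 names none.

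**Compliant examples.**

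- Platelets given on Day -9, platelet count on Day -8: meets the timing of 12c and does not breach exclusion 20.
- Red cells given on Day -16, hemoglobin on Day -15: meets 13 and does not breach exclusion 20.
- G-CSF given on Day -16, neutrophils on Day -15: meets the timing of 12b and does not breach exclusion 21.

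**Possible safeguards.** Inclusion 14 requires "Confirmation of patient eligibility for specific key criteria for study participation with the Medical Monitor", but sets no rule on support before the count. The word stable in criterion 13 governs only the exception above 8.0 g/dL. Footnote 5 permits a pre-dose C1D1 count without requiring one.

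**After the change.** If each interval is also counted back from the qualifying sample, the 14, 7 and 7 days become 0, 0 and 0.

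**The case against.** The strongest reply is that the C1D1 anchor is used consistently in 12c, 13, 20 and 21 and has a purpose of its own. The patient must reach first dose after one or two weeks without support, which keeps out those who currently depend on transfusion. The stated reason in Appendix 7 fits that reading too. The removal of the Day 1 date from criterion 13 also looks deliberate. This stands as far as it goes: the criteria do not contradict one another, and every patient must pass the support-free interval before dosing. It does not answer the point that the count used for entry may predate that interval.

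Several stronger readings are tempting, and the documents do not support them.

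- A reader might infer that all 21 screening days are equally exposed. That counts late samples where the support is almost a full interval old, such as platelets on Day -8 and a count on Day -2. Counts directly after permitted support are confined to 14, 7 and 7 days.
- A reader might take the missing date in criterion 13 to allow a hemoglobin of any age. Hemoglobin is part of the hematology panel (Section 9.4.3), and Table 1 places the baseline CBC at Screening or pre-dose on C1D1.
- A reader might conclude that a transfused hemoglobin defeats the selection suggested by Part 1, where time on study tended to be longer at 8.5 g/dL or above. Exclusions 20 and 21 came in only with Version 4, and nothing shows that the Part 1 values were free of support.
- A reader might attribute the 51% to Part 1. Part 1 enrolled 79 patients and the figure rests on 92.

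The shift-table effect is also conditional: any later pre-dose sample replaces the early one.

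**Conclusion.** The gap is real on the current text. A fully compliant patient can qualify on a platelet count drawn directly after a permitted transfusion on 14 screening days, and on a hemoglobin or neutrophil count drawn directly after permitted red cells or growth factor on 7. On the less-than wording the transfusion figures are 15 and 8. Only a sample on Day -1 or C1D1 is sure to come a full interval after the last permitted support, and on the less-than wording only C1D1.

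This rests on reading the criteria literally, with hemoglobin taken in the Table 1 window. It shows what is permitted, not what happened. That some patients began treatment with unsupported counts below the floors is possible but not shown, and the share affected is not given. The floors still bind patients who had no support and anyone sampled on C1D1. A reader might also infer a bias in the primary analysis. Nothing in the documents supports that, and the mITT population already admits patients with a sponsor waiver. The point concerns entry screening and hematology baselines, and it merits a short clarifying amendment.

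**What to change.** Reconcile the reference dates in inclusion 12 and 13, exclusions 20 and 21 and Table 1 footnote 5, in the body and the synopsis, leaving every threshold and interval as it is.

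1. State that each existing interval also applies to the qualifying sample for the count it affects: platelet transfusion to the platelet count, red-cell transfusion to hemoglobin, and each growth factor to its own cell line. The matching matters. A blanket sentence would make hemoglobin wait out a platelet-transfusion interval and neutrophils a red-cell interval.
2. As the alternative for recently supported patients, take the qualifying value from the pre-dose C1D1 CBC that footnote 5 already allows.
3. State in criterion 13 the sampling window that Table 1 implies for hemoglobin.
4. Have inclusion 12 refer to exclusion 21 as well as exclusion 20.

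The cost is a few sentences in an amendment and an extra CBC for recently supported patients. A few of them may be delayed or fail screening.
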